### **13.3 Patient Disposition in the Context of COVID-19**

If a patient develops active COVID-19 infection (whether confirmed or suspected) during the course of the study, the Investigator will work with the Medical Monitor to determine the best course of action, taking into consideration the AE and SAE guidelines in Section 11.0. If the study drug is discontinued or a patient is withdrawn from the study because of COVID-19, the reason for early termination will be captured in the EDC system as such.

### **13.4 Regulatory and Oversight Considerations in the Context of COVID-19**

If planned onsite monitoring visits are not possible because of COVID-19, remote monitoring may occur, if allowed by local and federal legal and regulatory requirements. If source data are collected at a home health visit, those source documents will be maintained with the homecare staff until they can be transferred to the trial site. If a protocol deviation is the result of COVID-19-related circumstances, this information should be captured. The impacts of these implemented contingency measures on the outcomes of this study, including any protocol deviations that result from COVID-19 illness and/or COVID-19 control measures will be discussed in the Clinical Study Report .

## 15.0 APPENDICES

### 15.1 APPENDIX I – Clinical Laboratory Evaluations

#### Chemistry [Fasted]:

Albumin  
Alkaline phosphatase  
ALT  
AST  
BUN  
Calcium  
Chloride  
Cholesterol  
Creatinine  
Calculated creatinine clearance  
GGT  
Glucose  
LDH  
Phosphorus  
Potassium  
Sodium  
Total bilirubin  
Total CO2 (measured as bicarbonate)  
Total protein  
Triglycerides  
Uric acid

#### Hematology:

Hematocrit  
Hemoglobin  
MCH  
MCHC  
MCV  
Platelet count  
Red blood cell count (RBC)  
White blood cell count (WBC)  
White blood cell differential (% and Abs):  
– Basophils  
– Eosinophils  
– Lymphocytes  
– Monocytes  
– Neutrophils

#### Other:

Glycated hemoglobin (HbA1c)  
Urine pregnancy test (FOCBP only): point-of-care pregnancy test  
SARS-CoV-2 (COVID-19) Qualitative PCR  
Vitamin B12 and serum paraproteins

#### Complete Urinalysis:

Color and appearance  
pH  
Specific gravity  
Bilirubin  
Glucose  
Ketones  
Leukocytes  
Nitrite  
Occult blood  
Protein  
Microscopic (including RBCs and WBCs)

#### Urine Drug Screen: point-of-care drug test

#### Serology

Hepatitis B surface antigen  
Hepatitis C virus antibody  
Human immunodeficiency virus antibody

## **15.2 APPENDIX II – Suicidal Ideation/Behavior Screening**

The Columbia-Suicide Severity Rating Scale (C-SSRS) is a validated questionnaire that helps to identify suicidal ideation and behavior (Posner, 2011) in clinical and research settings. The C-SSRS is referred to in the General Recommendations section of the FDA Guidance for Industry on Suicidal Ideation and Behavior: Prospective Assessment of Occurrence in Clinical Trials (Draft Rev 1; Aug 2012). The scale consists of two sections, one to assess suicidal intent or ideation and the other to assess suicidal behavior. Each section asks a small number of yes/no questions followed by scoring to quantify the intensity of ideation or behavior.

Two versions of the C-SSRS will be used in this study: Screening version (3 months and lifetime history) and the Since Last Visit version. The Screening version will be administered at the Screening visit. The Since Last Visit version of the C-SSRS will be administered at all subsequent assessment times. An investigator must review the C-SSRS data for each visit prior to the patient leaving the site and confirm that the patient did not express suicidal ideation or behavior that would require intervention.

### Suicidal Ideation

There are 5 yes/no questions in the ideation section of the questionnaire that capture 1) a wish to be dead or not wake up, 2) non-specific thoughts of suicide, 3) specific thoughts of suicide method without intent to act, 4) some intent to act but without a specific plan, and 5) active ideation with specific plan and intent. When the patient responds yes to any of the ideation questions, the most severe (i.e., 1 – 5) ideation is further characterized on a scale of 0 – 5 with regard to frequency, duration and controllability of thoughts, as well as deterrents to and reasons for ideation.

### Suicidal Behavior

The yes/no questions in the behavior section of the questionnaire ask about actual, interrupted, and aborted suicide attempts, as well as preparatory actions and non-suicidal injurious behaviors. The lethality of actual attempts is assessed on a scale of 0 – 4, and the potential lethality of non-lethal events (i.e., lethality = 0) is rated on a scale of 0 – 2.

### Study Application

In this study, the C-SSRS will be used both to screen potential study candidates for suicidal ideation/behavior and to monitor enrolled patients for suicidality during the Treatment period.

At Screening, potential candidates who meet either of the following C-SSRS criteria will be excluded from study participation:

1. Yes response to Question 4 (some intent to act but without a specific plan) or 5 (active ideation with specific plan and intent) in the Suicidal Ideation section, or
2. Yes response to any of the Suicidal Behavior questions, including preparatory actions or injurious behaviors, for the 3 month period prior to Screening.

Furthermore, these same criteria will result in patient discontinuation if observed during the Treatment period (see Section 7.7).

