	

4. Presence of any neuropathy other than DPN and/or significant risk factors for neuropathy other than diabetes, including Charcot Marie Tooth disease; alcohol abuse; B12 deficiency not adequately treated; uncontrolled hypothyroidism; evidence of paraproteins by serum immunofixation; history of chemotherapy with neurotoxic agents such as platinum analogs, taxanes, vinca alkaloids, eribulin, bortezomib and other proteasome inhibitors; or immunomodulatory agents such as thalidomide, lenalidomide, pomalidomide, neurotoxic check-point inhibitors, or any other chemotherapy known to have neurotoxic effects.

5. Other pain conditions that could confound the results of this study, or other chronic pain condition(s) that could affect compliance with pain medication restrictions or confound pain assessments. In addition to a general history and clinical examination, this will be assessed using the Masquerading Disorders Tool (MDT). Patients who screen positive on this tool for a potentially confounding disorder must be discussed with and approved by the Sponsor's Medical Monitor prior to being randomized into the study.

6. Painful DPN patients who have undergone lower limb amputations, are non-ambulatory, or whose walking is so impaired as to require a walker or other assistance for ambulation. Individuals whose neuropathy is so severely advanced as to create a significant risk that the neuropathy will be poorly responsive to treatment as defined by a Utah Early Neuropathy Scale (UENS) score > 24 at the time of Screening are also excluded from participation.

7. Have met Diagnostic and Statistical Manual of Mental Disorders V (DSM V) criteria for opioid use disorder or DSM V criteria for alcohol use disorder (moderate or severe) within the past 2 years.

8. Opioid use at a dose of <math>\geq</math> 30 morphine milligram equivalents on 3 or more days a week during the month prior to Screening.

9. Active suicidal ideation or suicidal behavior as assessed by the Investigator and/or by a rating of 3 or greater on the Columbia Suicide Severity Rating Scale (C-SSRS; see Appendix II).

10. The use of marijuana or cannabidiol (CBD) during the 30 days prior to starting study drug.

11. A positive urine screen for illicit or non-prescribed controlled substances at baseline.

--	--

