### 7.3.2 Exclusion Criteria

Patients meeting any of the following criteria will be excluded from the study:

1. Females who are pregnant or lactating.
2. Extremely overweight, defined as  $BMI > 40 \text{ kg/m}^2$ .
3. Difficulty understanding instructions for diary use as determined by the Investigator or other issues that are likely to make compliance with study requirements difficult.

4. Presence of any neuropathy other than DPN and/or significant risk factors for neuropathy other than diabetes, including Charcot Marie Tooth disease; alcohol abuse; B12 deficiency not adequately treated; uncontrolled hypothyroidism; evidence of paraproteins by serum immunofixation; history of chemotherapy with neurotoxic agents such as platinum analogs, taxanes, vinca alkaloids, eribulin, bortezomib and other proteasome inhibitors; or immunomodulatory agents such as thalidomide, lenalidomide, pomalidomide, neurotoxic check-point inhibitors, or any other chemotherapy known to have neurotoxic effects.
5. Other pain conditions that could confound the results of this study, or other chronic pain condition(s) that could affect compliance with pain medication restrictions or confound pain assessments. In addition to a general history and clinical examination, this will be assessed using the MDT. Patients who screen positive on this tool for a potentially confounding disorder must be discussed with and approved by the Sponsor's Medical Monitor prior to being randomized into the study.
6. Painful DPN patients who have undergone lower limb amputations, are non-ambulatory, or whose walking is so impaired as to require a walker or other assistance for ambulation. Individuals whose neuropathy is so severely advanced as to create a significant risk that the neuropathy will be poorly responsive to treatment as defined by a UENS score > 24 at the time of Screening are also excluded from participation.
7. Have met DSM V criteria for opioid use disorder or DSM V criteria for alcohol use disorder (moderate or severe) within the past 2 years.
8. Opioid use at a dose of  $\geq$  30 morphine milligram equivalents on 3 or more days a week during the month prior to Screening.
9. Active suicidal ideation or suicidal behavior as assessed by the Investigator and/or by a rating of 3 or greater on the C-SSRS (see [Appendix II](#)).
10. The use of marijuana or CBD during the 30 days prior to starting study drug.

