C-SSRS: Response of “yes” to suicidal ideation questions 4 or 5; or response of “yes” to any suicidal behavior questions	
 
For C-SSRS response of yes to suicidal ideation items: evaluate and ensure patient’s immediate safety; ensure patient has appropriate mental health follow up and any necessary intervention to assure patient’s safety. If patient describes intent to act or formed plan (i.e., more than passive suicidal ideation), discontinue patient from study treatment, ensure appropriate mental health follow-up and schedule for safety follow-up.
 

Cardiac Function	

New onset symptomatic bradycardia observed during Treatment period; i.e., heart rate < 50 bpm with weakness, confusion, shortness of breath, chest pain or hypotension, or evidence of new onset (i.e., not previously diagnosed) congestive heart failure	

For bradycardia, repeat measurements at least 30 minutes later to confirm. For confirmed bradycardia or new onset congestive heart failure, stop study drug and initiate appropriate medical workup.

If no underlying, non-study drug-related cause can be ascertained, no further study drug should be administered, study discontinuation measures should be obtained, and the patient should be followed until resolution.

--	---

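### The C-SSRS entry exclusion is stated at two different levels, and a suicidal-behaviour response on treatment has a stated discontinuation action in Appendix II but not in the 11.10.2.2 table

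*Protocol*

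**What the plan says.** **Entry.** Criterion 9 in Protocol 7.3.2 reads "Active suicidal ideation or suicidal behavior as assessed by the Investigator and/or by a rating of 3 or greater on the C-SSRS". The synopsis has the same cut-off, "by a rating of 3 or greater on the Columbia Suicide Severity Rating Scale", and SAP Exhibit 2 repeats it. The synopsis and 7.3.2 both refer the reader to Appendix II at that point.

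Appendix II, under Study Application, lists two exclusions at Screening. The first is a "Yes response to Question 4 (some intent to act but without a specific plan) or 5" in the ideation section. The second is a "Yes response to any of the Suicidal Behavior questions, including preparatory actions or injurious behaviors, for the 3 month period prior to Screening". The ideation items are defined earlier in the same appendix: "3) specific thoughts of suicide method without intent to act, 4) some intent to act but without a specific plan".

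**On treatment.** Appendix II says that "these same criteria will result in patient discontinuation if observed during the Treatment period", with a reference to Section 7.7. The table in Protocol 11.10.2.2 has the same triggers in its first column: ideation question 4 or 5, or any behaviour question. Its action column is introduced as applying to positive ideation items. It asks for evaluation, immediate safety measures and mental health follow-up, and then says: "If patient describes intent to act or formed plan (i.e., more than passive suicidal ideation), discontinue patient from study treatment".

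**The concern.** Criterion 9 and the appendix it refers to give different cut-offs for the same instrument at the same visit. On treatment, the appendix makes a behaviour response a ground for discontinuation. The monitoring table, where an investigator would look for the required action, lists that response as a trigger but does not say what to do about it.

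The stakes concern safety conduct and consistency across about 50 sites:

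- Suicidality is an event of special interest (Protocol 11.10.2.2, SAP 4.4.1), and Appendix II requires an investigator to review the C-SSRS before the patient leaves each visit. The rule has to be clear at that moment.
- Under Protocol 11.10.1.2 the DMC receives ad hoc unblinded case data when a patient is discontinued for an event of special interest. Whether a behaviour response leads to discontinuation therefore also decides whether that report is made.
- The per-protocol population (SAP 6.1.2) requires all eligibility criteria to be met. A patient entered on the Appendix II wording with item 3 as the highest item would breach criterion 9 and be removed from it.

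**Working it through.** No power or alpha calculation applies, and the plan gives no figure to reproduce. The check sets the rules side by side over every combination of highest ideation item (0 to 5) and suicidal behaviour (no or yes): 6 × 2 = 12 profiles. Three assumptions are made. A rating of 3 or greater is read as highest ideation item ≥ 3. Behaviour means recent behaviour, within the Appendix II window at entry. Where behaviour is present, the investigator is taken to identify it under criterion 9.

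**Entry**

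| Highest item | Behaviour | Criterion 9 | Appendix II |
|---|---|---|---|
| 0, 1, 2 | no | not excluded | not excluded |
| 3 | no | **excluded** | **not excluded** |
| 4, 5 | no | excluded | excluded |
| 0 to 5 | yes | excluded | excluded |

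Criterion 9 excludes 3 (items 3 to 5, no behaviour) + 6 (any item, behaviour) = 9 of 12. Appendix II excludes 2 + 6 = 8 of 12. The difference is 9 − 8 = 1 profile: item 3 without recent behaviour.

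**On treatment**

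| Highest item | Behaviour | Appendix II | 11.10.2.2 table |
|---|---|---|---|
| 0 to 3 | no | no trigger | no trigger |
| 4, 5 | no or yes | discontinue | discontinue |
| 0 to 3 | yes | **discontinue** | **trigger met; no express discontinuation** |

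Appendix II requires discontinuation in 4 (items 4 and 5, with or without behaviour) + 4 (items 0 to 3 with behaviour) = 8 of 12. The table states it expressly in 4 of 12, since items 4 and 5 carry intent by the appendix's own definition. The difference is 8 − 4 = 4 profiles.

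Within those four, the gap is complete when no ideation item is positive: the action text then has nothing to attach to. With items 1 to 3 positive, the evaluation and follow-up text can be read to apply, but discontinuation depends on intent or a plan. The table's gloss about more than passive ideation might be stretched to item 3, which is a further ambiguity.

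**Two faults in the Appendix II wording.** Its behaviour criterion is tied to the three months before Screening, so carrying over the same criteria to the treatment period cannot be done literally. And Section 7.7, to which it refers, lists general reasons for discontinuation and contains no C-SSRS rule.

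The 12 profiles are not equally likely, so these counts show where the texts differ, not how many patients are involved.

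**The case against.** A reader might infer that the same patient is both excluded and eligible. The documents do not support that. Section 7.3.2 excludes anyone who meets any listed criterion, and Appendix II nowhere says that a candidate outside its two conditions is admitted. Applied together, the rules exclude the item 3 candidate if rating means item. The reference to Appendix II may also be only a pointer to the instrument, because it follows the name of the scale. This objection stands against the stronger reading. What remains is that the appendix states its own exclusion rule for the same scale at a different level, so a site following the reference finds another cut-off.

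A reader might also infer that the discontinuation thresholds contradict each other, or that a stricter level at entry than on treatment is itself an error. Neither holds. The triggers in the table and the appendix agree, items 4 and 5 lead to the same result, and different levels for entry and continuation are not inconsistent in themselves.

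It can further be said that the table is merely incomplete and that Appendix II fills the gap, with Section 7.7 giving general cover for a patient at substantial risk. This has force: a site that reads both places can reach an answer. But the text that fills the gap has a behaviour window ending at Screening and refers to a section without the rule.

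Finally, because rating is undefined, the exact discordant group depends on the reading. That is correct, and it is one of the things to settle.

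**Conclusion.** The point holds as two limited inconsistencies. At entry, criterion 9 and Appendix II state different exclusion levels. If rating means the ideation item, they differ for one profile of 12: highest item 3 without recent behaviour. Another reading of rating would change that group but would still leave the two texts unaligned. On treatment, they differ for four profiles of 12: behaviour present with highest item 0 to 3, where Appendix II requires discontinuation and the table does not expressly state it.

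It would go too far to say that every candidate with item 3, or every patient with a behaviour response, is affected. A candidate with item 3 and recent behaviour is excluded under both texts, one whom the investigator judges to have active ideation is excluded by criterion 9 in any case, and a patient with behaviour plus item 4 or 5 is discontinued under both.

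The documents give no basis for estimating how many patients fall in the discordant groups. The primary analysis, sample size and error rate are untouched. The point deserves correction because it concerns a safety rule and the correction is easy. No view is taken on which threshold or action is right.

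**What to change.** - Reconcile the synopsis, Protocol 7.3.2, Appendix II (Study Application) and SAP Exhibit 2 so that one C-SSRS exclusion threshold is stated, and define what rating refers to (ideation item or intensity score).
- Reconcile the 11.10.2.2 table, Appendix II and Section 7.7 so that the on-treatment action for each listed trigger is the same in all places. This includes the period to which the behaviour criterion applies on treatment and the reference to 7.7.

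The threshold and the action are the sponsor's clinical decision. The cost is a wording amendment to the protocol, a matching line in SAP Exhibit 2 and a clarification to sites. No analysis changes.

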## Abbreviations

---

AE	adverse event
ALT	alanine transaminase
ANCOVA	analysis of covariance
AST	aspartate aminotransferase
ATC	anatomical therapeutic chemical
BDR	blinded data review
BMI	body mass index
BPI-SF	Brief pain inventory questionnaire – short form
CBD	cannabidiol
COVID-19	coronavirus disease 2019
CS	cumulative sum
CSR	clinical study report
C-SSRS	Columbia-Suicide Severity Rating Scale
DBP	diastolic blood pressure
DN4	Douleur Neuropathique 4 Questions
DPN	diabetic peripheral neuropathy
DSM V	Diagnostic and Statistical manual of Mental Disorders
ECG	Electrocardiogram
ESI	Event of special interest
FAS	full analysis set
FOCBP	female of child-bearing potential
FSH	follicle stimulating hormone
HbA1c	Glycated hemoglobin
HbsAg	hepatitis B virus surface antigen
HCV	hepatitis C virus
HDAC6	histone deacetylase 6
HIV	Human immunodeficiency virus
IB	Investigator brochure
ICF	informed consent form
ICH	International Council for Harmonisation
IENFD	Intraepidermal nerve fiber density
ITT	intent to treat

---

## Abbreviations, continued

---

MAR	missing at random
MDT	masquerading disorders tool
MedDRA	Medical Dictionary for Regulatory Activities
MINI	Mini-Mental State Examination
MMRM	mixed model repeated measure
NCS	normalized cumulative sum
NRS	numerical pain rating scale
NTSS-6	neuropathy total symptom score - 6
PCR	polymerase chain reaction
PGIC	patient global impression of change
PPP	per protocol population
pSAF	pre-randomized safety population
QOL-DN	Norfolk diabetic quality of life – diabetic neuropathy
SAE	serious adverse event
SAF	safety population
SAP	statistical analysis plan
SARS-CoV-2	severe acute respiratory syndrome coronavirus 2
SBP	systolic blood pressure
TEAE	treatment emergent adverse event
UENS	Utah Early Neuropathy Score
ULN	upper limit of normal
WHO	World Health Organization

## 1. Introduction

This statistical analysis plan (SAP) describes the planned analyses for Regenacy's Protocol REGY-DN-201, entitled "A Phase II, Randomized, Double-Blind, Placebo-Controlled, Parallel Group Study of Ricolinostat in Patients with Painful Diabetic Peripheral Neuropathy". This SAP is based on version 5 of the protocol, dated September 24, 2021.

This SAP is to be interpreted in conjunction with the protocol. Should the SAP and protocol be inconsistent with respect to the planned analyses, the language of the SAP is governing. If the final clinical study report (CSR) contains changes to any planned statistical analyses, the justification for any such differences will be fully documented in the CSR.

The statistical principles applied in the design and planned analyses of this study are consistent with the International Conference on Harmonization (ICH) guidelines E9 (Statistical Principles for Clinical Trials) [1].

## 2. Study objectives

### 2.1. Primary objective

The primary objective is to evaluate the safety and efficacy of ricolinostat compared with placebo for painful diabetic peripheral neuropathy (DPN) as measured by an 11-point numerical pain rating scale (NRS) after 12 weeks.

### 2.2. Key secondary objectives

The key secondary objectives are:

- Evaluating the efficacy of ricolinostat at 4 weeks as assessed by NRS, and
- Evaluating the efficacy of ricolinostat in improving non-pain neuropathic signs after 12 weeks as assessed by change in the UENS.

### 2.3. Secondary objective

The secondary objective of this study is to assess the efficacy of ricolinostat for non-pain diabetic peripheral neuropathic signs and to further assess efficacy in painful DPN.

#### **2.4. Exploratory objective**

The exploratory objective of this study is to assess the effects of ricolinostat on intraepidermal nerve fiber density (IENFD), a potential biomarker for efficacy, in a subset of patients with painful DPN treated with ricolinostat at 24 weeks.

